**Exclusion Criteria (EC):**

1. Received prior therapy with an anti-PD-1, anti-programmed cell death-ligand 1 (anti-PD-L1), anti-programmed cell death-ligand 2 (anti-PD-L2), anti-CD137, or anti-cytotoxic T-lymphocyte-associated antigen (CTLA)-4 antibody (including ipilimumab or any other antibody or drug specifically targeting T-cell co-stimulation or checkpoint pathways)  $\leq 12$  weeks prior to PVSRIPO infusion (note: does not apply for patients treated with pembrolizumab under this protocol who are eligible for PVSRIPO retreatment). Note: patients who had previously permanently discontinued any anti-PD-1 or PD-L1 therapy due to severe or life-threatening immune-related AE are excluded.
2. Excluded are:
  - a. Neoplastic lesions in the brainstem, cerebellum, or spinal cord
  - b. Radiological evidence of active/growing multifocal disease: no size increase  $> 0.5$  cm in any direction of any other enhancing non-target lesions present at baseline confirmed via most recent, prior, consecutive MRIs at least 3 months apart. However, two lesions totaling  $\leq 5.5$  cm of enhancing disease (total diameter) connected by T2 flair are not excluded
  - c. Tumors with  $\geq 1$  cm of contrast-enhancing tumor component crossing the midline (crossing the corpus callosum)
  - d. Extensive subependymal disease: multiple lesions or lesions covering  $> 50\%$  of subependymal space. Tumor touching subependymal space allowed
  - e. Extensive leptomeningeal disease: multiple lesions or lesions covering  $> 50\%$  of leptomeninges. Tumor touching leptomeninges allowed
3. Has received systemic immunosuppressive treatments other than systemic corticosteroids (eg, methotrexate, chloroquine, azathioprine) within six months of PVSRIPO infusion.
4. Requires treatment with high dose systemic corticosteroids, defined as dexamethasone  $> 4$  mg/day or equivalent, within 2 weeks of PVSRIPO infusion.
5. Prior interstitial brachytherapy, implanted chemotherapy, stereotactic radiosurgery or therapeutics delivered by local injection or convection enhanced delivery (CED), including PVSRIPO (except for qualifying patients being retreated with PVSRIPO within this trial).

[figure not shown]
	
 
6. Pregnant and/or breast feeding female; patient/female partner of childbearing potential who is unwilling to utilize protocol-defined acceptable form of contraception for duration of study.
 
7. Impending/life-threatening cerebral herniation syndrome, per neurosurgeon/designate.
 
8. Severe, active co-morbidity, defined as follows:             
 
a. Infection requiring IV treatment/unexplained febrile illness (maximum temperature (<math>T_{max}</math>) > 99.5°F/37.5°C)
 
b. Known immunosuppressive disease/human immunodeficiency virus infection
 
c. Known active hepatitis B (HBV) or C (HCV) infection via positive viral Deoxyribonucleic Acid (DNA) or Ribonucleic Acid (RNA), respectively
 
d. Unstable or severe intercurrent medical conditions such as severe heart disease (New York Heart Association Class 3 or 4)
 
e. Known lung disease with forced expiratory volume in 1st second of expiration < 50%
 
f. Uncontrolled diabetes mellitus (eg, hemoglobin A1C level > 7.0% with treatment)
 
g. History of other malignancy requiring active treatment within 2 years of biopsy/catheter placement with the exception of those with a negligible risk of metastasis or death (eg, resected cutaneous basal cell carcinoma, or other cancers with 5-year overall survival (OS) of > 90%)
 
 
 
9. Known albumin allergy.
 
10. Uncontrolled unexplained bleeding and/or hemoptysis within 4 weeks of biopsy/catheter placement.
 
11. Inability to undergo brain MRI with and without contrast. History of severe/anaphylactic reaction to gadolinium contrast agent is excluded. Mild allergy (eg, rash) acceptable with prophylactic acetaminophen and diphenhydramine.
 
12. History of neurological complications due to PV infection.
 
13. Not recovered from toxic side effects (alopecia acceptable) and/or no current or prior tumor treatments within the following timeframe relative to biopsy/catheter placement:             
 
a. Chemotherapy or bevacizumab <math>\leq</math> 4 weeks (except for nitrosourea [6 weeks] or metronomic dosed chemotherapy such as daily temozolomide, etoposide or cyclophosphamide [1 week])
 
b. Tumor treating fields <math>\leq</math> 7 days
 
c. RT of brain <math>\leq</math> 12 weeks, except for progressive disease outside of the radiation field or 2 progressive scans at least 4 weeks apart or histopathologic confirmation
 
 
 
14. History of agammaglobulinemia.
 
15. Known hypersensitivity to pembrolizumab, or any components of pembrolizumab.
 
16. Active autoimmune disease requiring systemic immunomodulatory treatment within the past 12 months; physiologic replacement therapy (eg, thyroxine, insulin, or physiologic corticosteroid replacement therapy for adrenal or pituitary insufficiency) is not considered a form of systemic treatment.
 

--	--

Concomitant Treatment	
Pembrolizumab: 200 mg given via IV infusion every 3 weeks (q 3 weeks) up to a maximum of 24 months.
 
As needed at Investigator discretion for the management of events noted below:
 
Bevacizumab and/or dexamethasone:
 
Based on previous studies, the recommended best standard of care (BSC) for control of PTE or CE-related sequelae after PVSRIPO infusion and/or combination of PVSRIPO and pembrolizumab, as needed, are:
 
 
• Preferred <math>\geq</math> 2 weeks post-PVSRIPO infusion: low dose bevacizumab (7.5 mg/kg q 3 weeks) 
 
○ Treatment with bevacizumab for the shortest course possible is desired over dexamethasone use for control of PTE or CE, when deemed safe to use by the investigator
 
○ Treatment with higher doses of bevacizumab for <math>></math> 2 cycles is not permitted per protocol
 
 
 
• Within 2 weeks of PVSRIPO infusion or thereafter, at the treating clinician's discretion if rapid results are required: low dose dexamethasone (<math>\leq</math> 4 mg/day) 
 
○ As low a dose as possible, for the shortest duration possible is desirable for managing PTE or CE. However, participants should primarily be managed with bevacizumab, thereafter
 
 
 
• Other supportive care treatments (eg, anti-epileptics for seizure)
 
 
For the management of any immune-related AE (irAE) after the first dose of pembrolizumab, as low a dose as possible of dexamethasone (ideally <math>\leq</math> 4 mg/day), for the shortest duration possible, is desirable. Patients requiring <math>></math> 4 mg/day of dexamethasone or equivalent prior to the first dose of pembrolizumab will be replaced.
 
Any irAE should ultimately be managed at the investigator's discretion with patient safety as the primary consideration.

Investigational Product(s)	PVSRIPO: Oncolytic Polio/Rhinovirus Recombinant; $5 \times 10^7$ tissue culture infectious dose (TCID) 50 delivered via CED intratumorally
Reference Product (comparator)	No active comparator at study outset (may be adapted to include a randomized comparator in the future); comparisons may be made to external controls in similar rGBM populations treated with PVSRIPO alone, pembrolizumab (or other anti-PD-1/ICI) alone or other to treatments/combination of treatments.
Planned Study Sites	Approximately 10
Criteria for Evaluation	
Laboratory and clinical evaluation including physical examination, KPS, neurological examination (including via the NANO scale) [8], assessment of AE and survival, as well as radiographic evaluations, will be assessed at regular intervals to evaluate safety and efficacy.
 
Biological samples, including blood/blood cells and tumor biopsy tissue (when available) will be collected to evaluate exploratory assessments of immune/genetic markers and other factors that may impact response.

Statistical Methods	
This single-arm study is designed to evaluate the efficacy, safety and tolerability of PVSRIPO when followed by pembrolizumab treatment in patients with rGBM. Summary statistics (eg, n, %, confidence intervals [CI]) will be employed to describe the key findings (ORR, DOR, incidence and severity of DLT, Grade 3 or higher AE, etc.).
 
Adverse events considered related to screening or other pre-infusion procedures that are not standard of care (eg, PV booster, biopsy prior to infusion, catheter placement without PVSRIPO infusion) will be summarized separately from TEAE (after PVSRIPO infusion), as will data from patients receiving only PVSRIPO and not at least one dose of pembrolizumab. The number of doses of pembrolizumab received and other baseline characteristics will also be explored as variables for safety and efficacy (eg, age, number of prior recurrences, KPS, NANO score, extent of prior resection, prior bevacizumab and chemotherapy use, tumor genetic profile).
 
All patients enrolled and treated with PVSRIPO will be summarized in all analyses. In addition, a per-protocol analysis will also explore the impact of excluding patients meeting pre-defined criteria from radiographic and survival analyses as outlined in Section 8. For comparisons of efficacy or safety relative to PVSRIPO alone or pembrolizumab alone from other data sources, both the overall and per-protocol populations may be considered.
 
The statistical analysis plan (SAP) will provide additional detail regarding planned statistical summary methods and analyses.

Determination of Sample Size	
Based on an interim summary of the Phase 1 study data of PVSRIPO in rGBM (Pro00031169), an ORR of 11.5% was demonstrated (7/61 patients). With 30 subjects treated in this study, there is >75% power to demonstrate a 20% or greater improvement in ORR with the addition of pembrolizumab (ORR > 31%, two-sided P<0.05).
 
The planned evaluable sample size of 30 patients will allow initial assessment of the anti-tumor response via the criteria noted in Table 3 and survival over time, to inform future study adaptations and/or the sample size and study design of new trials. The design will also allow for assessment of the efficacy, safety and tolerability of PVSRIPO plus pembrolizumab, relative to accumulated experience with PVSRIPO alone (eg, [5], data on file, Istari) and published or other data available with pembrolizumab alone in patients with rGBM (eg, [3]).

Study and Treatment Duration	
Maximum planned duration of follow-up: Up to 24 months (104 weeks). Participants achieving 24 months of follow-up may be offered participation in a roll-over protocol or other mechanism for longer-term follow-up.
 
Planned treatment duration:
 
 
Single PVSRIPO infusion at baseline (retreatment allowed for qualifying patients (ie, no ongoing AE <math>\geq</math> Grade 2 related to peritumoral edema, tolerated initial PVSRIPO infusion well) with enhancing disease <math>\geq</math> 6 months from initial PVSRIPO infusion (with or without post-infusion resection <math>\geq</math> 4 weeks after retreatment); see Section 3).
 
Pembrolizumab (200 mg IV infusion), q 3 weeks up to Week 104 (maximum of approximately 102 weeks of treatment), or until irAE meeting criteria for discontinuation or confirmed progression via criteria noted in Table 3).
 


Treatment interruption/discontinuation with pembrolizumab:
 
Adverse events of an immunologic etiology, including infusion related reactions, have been associated with pembrolizumab exposure. Depending on the severity of the irAE, pembrolizumab should be temporarily withheld or permanently discontinued as outlined in Section 7.5.3 and the most recent Keytruda® (pembrolizumab) package insert (PI) and “Guide for Keytruda®” provided in the study administration manual (SAM).
 
In general, for an irAE requiring dose interruptions, low-dose dexamethasone (<math>\leq 4</math> mg/day) should be initiated and tapered when the irAE is <math>\leq</math> Grade 1.
 
For patients with irAE meeting dose interruption criteria, the next dose of pembrolizumab will be withheld until the irAE has been reduced to <math>\leq</math> Grade 1 and dexamethasone (or equivalent) dose has been tapered to <math>\leq 4</math> mg/day and/or discontinued.
 
Pembrolizumab should be permanently discontinued for severe infusion-related reactions and for irAE that do not resolve within 12 weeks of the last dose of pembrolizumab or dexamethasone (or equivalent) cannot be reduced to <math>\leq 4</math> mg/day within 12 weeks.
 
Subjects who discontinue pembrolizumab should continue to be followed until resolution of AEs and for clinical outcomes, as detailed in Sections 5.4 through 5.6.

--

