 Individuals of childbearing potential, pregnancy test (urine or serum) within 48 h of catheter placement. Repeat every 6 months or any time pregnancy suspected.

 Thyroid panel (at a minimum: TSH and free T4; may include free and total T3) should occur every 6 weeks while patient is receiving pembrolizumab.

 If undetectable anti-tetanus toxoid immunoglobulin G (ATT IgG) at screen, then Tdap booster vaccine > 1 week prior to biopsy/catheter placement.

 LSQ analysis should include the following (both %, and ABS): CD3 T, CD4 T, CD8 T, CD19 B, CD56 NK cells. LSQ should be collected at visit 1 (pre-boost), visit 2 (post-boost), and before pembrolizumab doses at visits 5 and 6.

 Collection of whole blood for biomarker analyses where indicated. Collected at visit 1 (pre-boost) and visit 2 (post-boost), before pembrolizumab doses at visits 5, 6, 8, and at End of Study visit for progression.

 MRI with and without contrast. Screening MRI conducted within 14 days prior to catheter placement. If neurologic deficit presents at visit 5 and pembrolizumab dose is held to days 15 to 28, MRI should be conducted and precede pembrolizumab administration. After week 11, MRI to occur every 9-12 weeks or more frequently, at the discretion of the treating physician.

 CT occurs before infusion to confirm placement criteria and after catheter is removed, post-infusion, to confirm no bleeding.

 If possible, up to 3 additional core biopsies will be obtained for biomarker testing (if not available from archival tissue obtained within 6 weeks).

 Results from an unscheduled or unplanned biopsy and/or surgical resection should be recorded in the eCRF, and remaining tissue may be requested for analysis.

 PVSIPO retreatment may be allowed for confirmed progression  $\geq$  12 months post-initial PVSIPO infusion with Sponsor/designee approval.

 All visit assessments should be conducted before pembrolizumab administration. Pembrolizumab should be administered every 3 weeks  $\pm$  1 week through week 104, with the first dose at day 14 but up to day 28, if required. If pembrolizumab is permanently discontinued, then safety laboratory evaluations that are not SOC are no longer required 30 days after the date of pembrolizumab discontinuation.

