### 5.7.2 Radiographic Imaging

A baseline MRI of the brain with and without gadolinium contrast must be conducted within 14 days of catheter placement for PVSRIFO infusion, but as close to biopsy/catheter placement as possible, and thereafter as scheduled in **Table 1**. Allowance will be made for the use of volumetric, contrast-enhancing imaging modalities as well, with Sponsor approval. Eligibility based on radiographic IC/EC will be based on the screening MRI obtained within 14 days of catheter placement; this MRI (and if required, recent prior MRIs) will be provided to the Sponsor or their designee for eligibility confirmation.

In addition, a CT scan will occur immediately after catheter placement in an effort to ensure proper positioning, and immediately after catheter removal post-PVSRIFO infusion, to confirm there is no bleed.

All MRI will be assessed by the investigator; tumor measurements and response will be recorded in the eCRF according to the response criteria outlined **Section 8.4.6.1** summarized in **Table 3**.

All de-identified images may be requested by the Sponsor for independent radiographic assessment and/or long-term storage.

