#### 6.5.4.2 Bevacizumab

A clinically important feature of bevacizumab is the steroid-like improvement of the disrupted blood-brain barrier and reduction in PTE and mass effect when use in rGBM [26-28]. Given this and the success utilizing bevacizumab for the management of PTE or CE and related sequelae in prior studies with pembrolizumab [3] and PVSRIPO [5] and the combination in rGBM patients treated under compassionate use, eligible participants will be allowed to initiate bevacizumab treatment (7.5 mg/kg q 3 weeks) as early as 2 weeks after PVSRIPO infusion, at the time of the first planned pembrolizumab treatment. Bevacizumab use should be reevaluated as soon as

possible but at a minimum, after 3 consecutive doses (9 weeks) and be discontinued as soon as possible at the treating clinician's discretion.

Intermittent, short-term, lower dose bevacizumab use is not anticipated to have an appreciable impact on survival outcomes based on limited anti-tumor activity [26-28]. Given the impact of bevacizumab on enhancing lesions [29], all radiographic response will be confirmed  $\geq$  8 weeks after discontinuation of bevacizumab to account for the known radiographic pseudoresponse and T2/Fluid-Attenuated Inversion Recovery (FLAIR) will be monitored over time by independent radiographic reviewers blinded to patient outcome and bevacizumab use.

Branded Avastin® (bevacizumab) is preferred but if unavailable, MVASI™ (bevacizumab-awwb) is an acceptable alternative (check with Sponsor before utilizing any others). Bevacizumab will not be provided by the study.

**Risks Associated with Use:** There is a warning and precaution noted in the prescribing information of bevacizumab regarding risks of bleeding/wound healing complications within 28 days following major surgery. For this protocol, investigators will have the discretion to use low-dose bevacizumab at  $\geq$  2 weeks following the less invasive biopsy/intracranial infusion, if such use is judged by the investigator to be less than the potential risk of sequelae associated with PTE or CE after PVSRIPO treatment alone and/or followed by pembrolizumab. Bevacizumab is also associated with thromboembolic and other events; see the PI.

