### **6. CHANGES IN THE PLANNED ANALYSES**

1. Day 0 is the earliest day that study drug is initiated but will be designated as Day 1 based on implementation standards for the analysis.
2. Central imaging review was not completed; therefore, results from this will not be presented.
3. The following analyses will not be completed:
  - a. Durable radiographic response (DRR)
  - b. Duration of disease control (DDC)
  - c. Progression-free survival (PFS)
  - d. Analysis of Per-Protocol population
  - e. Analyses based on participant strata (prior anti-VEGF agents, prior chemotherapy use)
  - f. Analyses on the efficacy set and PP set for the following subgroups: baseline NANO score, KPS, prior bevacizumab and chemotherapy or other treatment use/failure, extent of surgery at diagnosis, MGMT promoter methylation status and/or other tumor genetic factors at diagnosis and baseline, lesion cross-sectional area at baseline, number of prior progressions, age, gender.

- g. Landmark survival at month 24
- h. Exploratory analyses including analysis of efficacy based on modified iRANO criteria in Section 8.4.6.1, Table 3 of the protocol, identification of biomarkers of anti-tumor response to lerapolturev following by pembrolizumab or assessment of patient reported outcomes
- 4. The entire anticipated sample size of patients was not enrolled.

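### The protocol distrusts enhancement for 8 weeks after bevacizumab when it confirms response, but it allows a baseline MRI 15 days after the last dose, and the SAP applies the 8-week rule to neither scan

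*Protocol*

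**What the plan says.** **Washout.** Protocol exclusion criterion 13 (Synopsis and Section 4.2) requires "no current or prior tumor treatments within the following timeframe relative to biopsy/catheter placement". Item 13a sets the limit for bevacizumab at 4 weeks or less. The clock runs to catheter placement, not to the baseline scan.

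**Baseline MRI.** Table 1, footnote 13: "Screening MRI conducted within 14 days prior to catheter placement". Section 5.7.2 repeats the 14-day limit and adds "but as close to biopsy/catheter placement as possible".

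**Response scans.** Section 6.5.4.2 requires radiographic response to be confirmed at least 8 "weeks after discontinuation of bevacizumab to account for the known radiographic pseudoresponse". Table 3, item 4, applies the same 8 weeks to CR, PR and SD. Neither place mentions the baseline scan.

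**SAP criteria.** SAP Section 3.2.6 states that the efficacy definitions are iRANO without the Table 3 modifications. PR is a decrease of at least 50% held for at least 4 weeks, with no bevacizumab condition. PD is an increase of at least 25%, and no reference scan is named.

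**Subgroups.** Protocol Section 8.4.6 plans analyses both pooled and separately by prior anti-VEGF use. SAP Section 3.2.1 uses no strata, and Section 6, item 3e, lists among the analyses not to be done "Analyses based on participant strata (prior anti-VEGF agents, prior chemotherapy use".

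**The concern.** Response is a ratio of a later scan to a reference scan. The protocol accepts that bevacizumab distorts the measurement and waits 8 weeks before trusting the later scan, yet it sets no such wait for the reference.

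If enhancement at baseline is still suppressed, the lesion is recorded as too small. A true shrinkage of 50% then falls short of PR, and the return of enhancement as the drug wears off can look like growth. Best overall response, DCR and DOR could be affected. So could continuation of pembrolizumab, which ends at confirmed progression.

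The SAP opens the opposite problem. Low-dose bevacizumab is the preferred edema treatment from 2 weeks after infusion. Without the 8-week condition, a shrinkage caused by that treatment can count as PR. Two distortions of opposite sign would then sit in one pooled ORR, and no planned summary separates them.

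**Working it through.** **1. The plan's own figure.** Protocol Section 8.1 and SAP Section 3.1 give more than 75% power for an ORR of 31% against 11% (7/61 = 11.5%) with n = 30, two-sided P<0.05. By exact binomial, the smallest count with an upper tail of at most 0.025 is 8 of 30. The tail is 0.0135 at 11% and 0.0174 at 11.5%. P(X >= 8) at 31% is 75.7%, so the figure reproduces. The documents do not state an 8/30 rule; it is used here only as a yardstick.

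**2. Timing.** Bevacizumab up to day 28 before placement is excluded, so the earliest placement is day 29 after the last dose.

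- MRI at the 14-day limit: 29 - 14 = day 15, which is 56 - 15 = 41 days short of 8 weeks.
- MRI on the placement day: day 29, which is 56 - 29 = 27 days short.

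The patients at issue are those whose baseline MRI falls on days 15 to 55 after their last dose.

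**3. Effect on the thresholds (assumption: a fraction s of the lesion is suppressed at baseline; the documents give no value).** Shrinkage of the true lesion needed for PR is 1 - 0.5(1 - s). The apparent growth if suppression fully reverses is s/(1 - s).

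| s | True shrinkage needed for PR | Rebound over baseline |
|---|---|---|
| 10% | 55% | +11% |
| 20% | 60% | +25% |
| 30% | 65% | +43% |
| 50% | 75% | +100% |

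Rebound alone reaches the 25% PD threshold only if s is at least 20%.

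**4. Downward effect on ORR (assumption: k of 30 patients have their 31% response probability halved to 15.5%).** Observed ORR = [(30 - k) x 0.31 + k x 0.155]/30. P(X >= 8) comes from the sum of the two binomials.

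| k | Observed ORR | P(X >= 8) |
|---|---|---|
| 0 | 31.0% | 75.7% |
| 5 | 28.4% | 65.3% |
| 10 | 25.8% | 52.9% |
| 15 | 23.25% | 39.5% |

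**5. Upward effect on ORR.** Each pseudoresponse counted as PR adds 1/30 = 3.3 points, so two add 6.7. With k = 10 the expected loss is 10 x 0.155 = 1.55 responses, or 5.2 points, and two pseudoresponses would more than offset it. Such a PR is possible under the SAP: Section 6.5.4.2 calls for re-evaluation of bevacizumab at the latest after 3 consecutive doses (9 weeks), and the SAP's PR needs only 4 weeks. The requirement of stable or improved T2/FLAIR is a partial check. However, the independent review meant to follow T2/FLAIR was not completed (SAP Section 6, item 2).

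**The case against.** The strongest case against acting has several parts.

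- **Purpose.** An eligibility washout and a response-confirmation interval serve different ends and need not be equal. This stands as far as eligibility goes. It does not explain why the analysis should trust one scan of the pair at day 15 and distrust the other until day 56.
- **Entry criteria.** Patients must have actively growing, biopsy-confirmed tumor with an enhancing lesion of at least 1 cm, and the sponsor verifies size and location. Section 5.7.2 also asks for the MRI close to placement. Heavy suppression is therefore less likely, but neither a biopsy nor a minimum diameter shows that the measurement is free of drug effect.
- **Progression safeguards.** Within 6 months of starting immunotherapy, iRANO progression without a new or worse deficit needs confirmation at 3 months. This filters transient change, but enhancement that returns because the drug has worn off need not recede. PFS is no longer analysed, so that endpoint is not at risk.
- **Shared bias.** The documents do not give the Phase 1 washout behind 7/61. If it was similar, part of any bias lies in the benchmark too.

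Some stronger readings are tempting, and the documents do not support them.

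- A reader might infer that up to half the sample is affected. The 50% figure in Sections 4.2.1 and 8.4.6 counts any past anti-VEGF use, however old; only recent bevacizumab matters here.
- A reader might extend the 8-week rule to every anti-VEGF agent. The protocol states it for bevacizumab alone.
- A reader might conclude that the distortion is invisible. The SAP lists prior systemic therapy, lesion assessments and lesion response by participant, so it could be reconstructed by hand. Only a planned summary is missing.

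**Conclusion.** The inconsistency is established from the documents. A baseline MRI 15 days after bevacizumab is permitted, the 8-week rule never covers it, and the SAP removes the rule from response scans as well. For patients scanned on days 15 to 55 with enhancement still suppressed, response would be biased downward and apparent progression upward. For patients responding on, or soon after, on-study bevacizumab, response may be biased upward.

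The size is not established. The number recently exposed, the degree of suppression and the number of pseudoresponses are all absent from the documents. Under the assumptions shown, the downward effect runs from none to 7.75 points (31.0% to 23.25%). The extreme needs all 15 permitted prior anti-VEGF users to be recent bevacizumab users who lose half their responses. A reader might conclude that the trial's ORR is understated. The documents do not support that, because the two effects oppose each other and neither can be quantified. Nor should the falls in P(X >= 8) be read as lost power. The SAP is descriptive with Clopper-Pearson intervals, and its Section 6, item 4, says that the full sample was not enrolled, so the n = 30 figures only illustrate the planned design.

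**What to change.** Leave eligibility and treatment as they are and change the analysis.

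1. In SAP Section 5.7.1.2, add a sensitivity ORR with Clopper-Pearson intervals that applies the protocol's 8-week rule to both sides of the comparison:
   - flag participants whose last bevacizumab dose was less than 8 weeks before the baseline MRI, and report ORR with and without them;
   - where bevacizumab was given on study, count CR or PR only if it persists at least 8 weeks after bevacizumab stops.
2. Remove the prior anti-VEGF stratum from SAP Section 6, item 3e, and report ORR by that stratum as the protocol planned, as descriptive only.

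Both sides are needed: correcting the baseline alone would address only the distortion that lowers ORR.

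The sponsor should also reconcile the washout and MRI-window passages with the 8-week rule, or state why they differ.

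The cost is SAP wording and one extra table. Start and stop dates of prior and concomitant therapy are already captured (Protocol Section 6.5), and the lesion listings exist. The downside is small groups with wide intervals. If no participant is flagged and no response depends on bevacizumab, the table shows this and the point is closed.
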